# 8.1.5.9 Anesthesia and surgical positions

General anesthesia is performed using a double-lumen endotracheal tube with unilateral lung strengthening ventilation. The patient is in healthy lateral decubitus position, the operating bed is in "jackknife position" 30 °, the upper limb of the operating side is suspended on the anesthesia head frame, and the investigator operates on the side of the patient. After lobectomy, positive pressure ventilation of the affected lung is performed to fully expand the residual lung to avoid the presence of thoracoscopic illegible localized atelectasis.

#### 8.1.5.10 Surgical incision

Thoracoscopic lobectomy surgical incision, including 1 thoracoscopic cannula incision about 1.5 cm in length,  $1\sim3$  operating cannula incisions about 1.5 cm in length, or/and 1 chest wall-assisted small incision  $5\sim7$  cm in length.

- Thoracoscopic incision: generally selected between the 8th intercostal space and axillary midline. The choice of incision location varies slightly from subject to subject and from lobe to lobe.
- (2) Operating cannula incision: 1 ~ 2 (sometimes 3) operating cannula incisions are generally used; their positions can be determined after thoracoscopic exploration of the thoracic cavity, based on the principle of facilitating surgical operation. The retractor operation hole is generally selected near the posterior axillary line of the 7th and 8th intercostal spaces.
- (3) Small incision on chest wall: The location of small incision is generally selected between the anterior and posterior axillary line of the 5th intercostal space. In addition, it can be selected according to the surgical needs and resection of different lobes. The selection of small incision should generally follow the principles of proximity to the pulmonary hilum, less chest wall injury, and relatively beautiful scar of the incision.

#### 8.1.5.11 Treatment of hilar vessels and bronchi

(1) Anatomic lobectomy is shown under thoracoscopic visualization. The investigator lifts the adventitia with an atraumatic endoscopic grasper in one hand and endoscopic dissecting hook or endoscopic scissors in the other hand, divides the adventitia, bluntly separates the vessels, overhangs the traction line, lifts the vessels, ligates the pulmonary vessels with an endoscopic knotter or cuts the pulmonary vessels with an endoscopic vessel suture cutter under direct vision through a small chest wall incision, and the larger vessels can be treated by ligating them at the proximal end of the vessel and then cutting them with a cutting stapler. In order to reduce pulmonary congestion and pulmonary section oozing, the pulmonary artery can be firstly treated and the pulmonary veins can be postconditioned. Bronchial handling is usually performed after pulmonary vascular handling. The peribronchial tissues are lifted with endoscopic grasping forceps, the endoscopic dissecting hook is separated to the distal end of the resected bronchus, the peribronchial lymph nodes are removed, electrocoagulation is performed for hemostasis, the bronchial artery is clamped with endoscopic titanium staples, the bronchus is completely freed, the cutting surface is selected, the endoscopic bronchectomy stapler is inserted, the atretic bronchus is compressed. After the reload is examined as exact and complete, the bronchus is cut. The diseased lung is loaded into the specimen bag and removed through a small incision. Electrocoagulation or argon is adopted for hemostasis. The thoracic cavity is flushed, and the two-lung ventilation is changed. The lung is expanded to examine whether there is air leakage at the bronchial stump. The surgery is ended after the drainage tube is placed.

(2) Lobectomy with massive stapling of the hilum without retraction of the ribs. Thoracoscopy showed that the hilum was sharply and bluntly dissected to expose the lobar vessels and bronchi, the lung grasper lifted the lobe to be removed, the hilum was bypassed with a rubber catheter, the catheter was extracted from a chest wall incision, the thick tip of the catheter was placed on an endoscopic stapler to fire the stapler and staple the hilum. The stapler was then removed, the clip was reloaded, advanced through the incision into the thoracic cavity, the hilum was again jammed distal to the first stapling, and the stapler was fired. The lobe was excised from the distal end of the stapler, packed in a specimen bag, and removed from the small incision. Water was injected into the thoracic cavity to inflate the lung to check whether the stapling of bronchial stump was true or not. If there is no active bleeding and there is no air leakage at bronchial stump, place a closed drainage tube to end the operation.

## 8.1.5.12 Removal of lung specimens

The specimens shall be carefully removed through the incision by placing them in a specimen bag or sterile glove.

## 8.1.5.13 Lymphadenectomy

The lymph nodes and surrounding adipose tissue of each group shall be carefully dissected.

## 8.1.5.14 Chest tube placement and incision closure

Two upper and lower thoracic drainage tubes are placed for upper lobectomy, and lower thoracic drainage tubes are placed for lower lobectomy, both of which are placed through the endoscopic hole or operation hole. The upper thoracic drainage tube could be placed on the top of the chest along the lateral side of the lung; the placement of thoracic drainage tube should be performed under direct thoracoscopic vision. Intercostal nerve closure is performed with 1% bupivacaine in the upper and lower ribs of each incision to reduce postoperative pain. Under direct thoracoscopic assistance, the pleura and intercostal muscles are closed, followed by sequential suture of the chest wall tissue and finally suture of the cannula incision.

#### 8.1.5.15 Precautions

- Lobectomy should be based on the results of various examinations to preserve good lung tissue as much as possible.
- (2) The section should ensure that there is no lesion as far as possible. The tracheal stump should preferably be sutured with absorbable suture and embedded with the surrounding tissues to reduce the occurrence of stump fistula.
- (3) Pulmonary vascular injury should be prevented. Accidental vascular injury during surgery is common in cases of chronic pulmonary suppuration, with severe perivascular adhesions or interlobar fissure hypodifferentiation. In this case, it can be operated under direct vision through a small thoracic incision, the hilum is dissected with conventional thoracotomy surgical instruments, and the pulmonary vessels

are freed. Once major bleeding occurs, the bleeding site should be immediately compressed with gauze pieces and converted to thoracotomy in a timely manner.

- (4) The surgery procedures should be flexibly controlled. The anatomical characteristics of each lobe are different, and the operation sequence of thoracoscopic anatomical lobectomy is also different. Left lower lobe or right middle lobe and lower lobe resection is basically the same as conventional thoracotomy. The artery is firstly processed, the vein is then processed, and the bronchus are finally processed; for right upper lobe pneumonectomy, the posterior segmental artery of the upper lobe is firstly dissected. After cutting off, the upper lobe lung is pulled forward to process the upper lobe bronchus, the anterior branches of the upper lobe artery are then processed, and the upper lobe branches of the upper pulmonary vein are finally processed; for left upper pneumonectomy, the lingual artery through the interlobar fissure is generally separated and cut, the anterior and posterior branch arteries upwards are separated and processed, and then the upper pulmonary vein are for VATS pneumonectomy is basically the same as that of lobectomy, but the pulmonary vessels and bronchi are thick. Vascular treatment advocates proximal ligation and then cutting stapler.
- (5) Anti-tuberculosis drugs must be continuously taken to for at least half a year after surgery.

Note: The above treatment principles are only for the reference of the investigators, and the investigators can deal with them according to the actual situation.

#### 8.1.6 Selection of Subjects

#### 8.1.6.1 Clinical trial indications

At present, the Disposable Powered Articulating Endoscopic Linear Cutter Stapler can be used for "a variety of open or minimally invasive surgeries in general surgery, obstetrics and gynecology, urology, thoracic surgery and pediatrics. They can be used together with staple line or tissue supporting materials. They also can be used for transection and excision of liver parenchyma (hepatic vascular system and bile duct structure), pancreas, kidney and spleen.

However, according to the *Guidelines for Technical Review of Endoscopic Stapler Registration*, "the surgical site and/or tissue type and thickness selected for clinical trial shall cover the intended clinical applicable scope of the product under application", and the cutting and anastomosis of lung tissues are common uses of the device. Therefore, thoracic surgery is selected for the clinical trial.

At the same time, clinicians will use linear staplers when performing VAT anatomical lobectomy (segmentectomy) according to clinical research. Therefore, the indication of this clinical trial is: "**anatomic lobectomy (segmentectomy)**."

#### Lobectomy (segmentectomy) 8.1.6.2 Inclusion criteria

#### Subjects meeting all of the following conditions only can be included:

- (1) Subjects are aged 18-70 years (inclusive), male or female;
- (2) Subjects are scheduled to accept thoracoscopic anatomical lobectomy (segmentectomy);
- (3) Subjects or their guardians are able to understand the purpose of the study, show adequate compliance with the trial protocol, and sign an ICF.

#### 8.1.6.3 Exclusion criteria

#### Subjects meeting any of the following conditions can not be included:

- (1) Subjects are with video-assisted thoracoscopic surgery-related contraindications;
- Subjects' preoperative imaging findings indicate severe pleural adhesions and significantly calcified hilar lymph nodes;
- (3) Subjects with platelet (PLT)  $< 60 \times 10^{9}$ /L or international normalized ratio (INR) > 1.5;
- (4) Subjects with forced expiratory volume in one second (FEV1)/predicted value  $\leq$  50%, or forced expiratory volume in one second (FEV1)/forced vital capacity (FVC)  $\leq$  60%;
- (5) Subjects with ejection fraction  $\leq 50\%$ ;
- (6) Subjects with major organ failure or other serious diseases (including clinically relevant cardiovascular disease or myocardial infarction within 12 months prior to enrollment; severe neurological or psychiatric history; preoperative severe infection that must be controlled by medication; active disseminated intravascular coagulation; high risk of thrombosis);
- (7) Subjects who are pregnant or lactating women;
- (8) Subjects participating in other drug or device clinical trials within 1 month before the trial;
- (9) Other situations not suitable for inclusion judged by the investigators.

#### 8.1.6.4 Study termination criteria

Study termination refers to that the clinical study has not been completed according to the protocol, and all clinical studies are stopped halfway. The purpose of terminating the clinical study is to protect the rights and interests of the subjects and ensure the quality of clinical study. Except for Item 6 below, the sponsor and the investigators shall jointly negotiate whether to terminate the trial:

- If serious safety problems occur during the clinical study, the clinical study should be terminated in a timely manner;
- If the product is found to have no clinical value during the clinical study, the clinical study shall be terminated;
- (3) In the process of clinical study, it is found that the clinical study protocol has major errors and it is difficult to evaluate the product effect; or the protocol has serious deviation in the implementation, in

which it is difficult to evaluate the product effect if the study is continuously to be conducted, , the clinical study shall be terminated;

- (4) The sponsor requests to terminate the study (for reasons, e.g., financial, etc.);
- (5) The clinical trial institutions and investigators fail to comply with the laws and regulations related to clinical trial and clinical trial protocol, and fail to make correction after being pointed out, resulting in serious situations or failure to change.
- (6) NMPA orders to terminate the clinical study for some reason(s).

After the study is terminated, the investigators should continue to provide appropriate treatment for the subjects from the perspective of protecting the rights and interests of the subjects, and inform the subjects of the treatment received during the trial and related treatment in detail. The subject data continues to be acceptable for evaluating the safety of the product.

The investigators should timely feed back the termination of the subject study to the sponsor.

#### 8.1.6.5 Enrollment time

It is estimated that the first subject will be enrolled in August 2018. The total enrollment time is 6 months, and the trial end time for the last subject will be March 2019.

#### 8.1.6.6 Expected duration of clinical trial and the reasons for determination

The expected enrollment time for the first subject is August 2018. The enrollment time for subjects is 6 months. The time for the last subject to complete the trial is March 2019. The time for statistical analysis and preparation of study summary report after the completion of clinical trial is 2 months, and the total clinical study period is 8 months.

#### 8.1.6.7 Expected duration of participation of each subject

The expected screening period from signing the ICF to enrollment for each subject is 7 days, and the postoperative follow-up period is about 30 days. The total subject observation period is 37 days. If a subject experiences an adverse event during the clinical trial, the outcome of the adverse event needs to be observed.

#### 8.1.6.8 Number of subjects required for clinical trial

The total sample size is 164. See Section 9.2 for details.

#### 8.1.6.9 Drop-out criteria and treatment

Definition of drop-out: All the subjects who have signed the ICF and passed screening to enter the clinical trial, no matter when or when they withdraw from the study, will be called drop-out cases as long as they have not completed the observation period specified in the protocol.

Drop-out criteria:

 The subject is unwilling or impossible to continue the clinical trial for any reason, and the clinical trial is terminated by putting forward a request for withdrawal from the clinical trial to the investigator;

- (2) The subject is lost to follow-up due to no treatment or examination although the subject does not explicitly withdraw from the clinical trial;
- (3) If the subject experiences a serious adverse event (SAE), the investigator should withdraw the subject from the clinical trial;
- (4) Poor subject compliance.

Treatment of dropout cases: For all the dropout cases, it is necessary to fill in the summary form of completion of clinical trial in the case report form and analyze the reasons for dropout. When a subject dropped out, the investigator should contact the subject as far as possible, ask the reason and record the last clinical symptom, and complete the evaluation items that could be completed. When withdrawing from the study due to adverse events, the investigator should take appropriate treatment measures according to the actual situation of the subject.

When a subject or his/her guardian actively requests to withdraw from the trial, the subject or his/her guardian should be asked that whether the subject's previous data can be continuously used in the clinical trial, and whether the results can be recorded in the original records. When no enquiry is performed, the data are available by default.

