#### (5) Incidence of SAEs

Lobectomy (segmentectomy)

**Evaluation time:** During the whole clinical trial process.

**Evaluation method:** Serious adverse event refers to events occur in the process of clinical trial that causes death or serious deterioration of health, including fatal disease or injury, permanent damage to the body structure or body function, requiring hospitalization or prolonging the hospitalization, requiring medical or surgical intervention to avoid the permanent damage to the body structure or body function.

**Formula:** SAE incidence = number of subjects with SAE in this group/number of all subjects in this group  $\times$  100%.

**Precautions:** The adverse events related to the staple line during clinical trial shall be considered as serious adverse events. Since "staple line repair" may be associated with "staple line dehiscence", the "staple line repair "is not repeatedly considered a serious adverse event.

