## 9.7.2 Missing, unused, or incorrect data (including dropouts and withdrawals) and unreasonable data

All missing, unused or incorrect data (including dropouts and withdrawals) and unreasonable data will be discussed and finally determined by the investigators and biostatistician in the data review stage. The basic statistical principles for the processing of these data are as follows:

- (1) The details of each drop-out case shall be described, and the drop-out between the test group and the control group shall be compared using Pearson  $X^2$  test or Fisher exact test;
- (2) Missing data at baseline shall not be estimated;
- (3) Missing values of main evaluation indicator (success rate of device cutting and anastomosis) shall not be estimated;
- (4) Missing values of secondary evaluation indicators shall not be estimated;
- (5) The wrong and unreasonable data shall be regarded as missing values;
- (6) Missing values for all safety measures shall be estimated using the worst case;
- (7) Sensitivity analysis shall be performed on the safety data set for all the safety evaluation indicators after treatment.

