#### 14.1.3 Reporting and handling of adverse events

All the adverse events and serious adverse events observed in the clinical trial should be clearly filled in the adverse event column of case report form. The duration of adverse event (i.e., the date of occurrence and disappearance of adverse event), severity, relationship with the clinical trial, and corresponding treatment and other handling measures should be recorded. Subjects occurring such event shall be followed up to end of the trial or the adverse event outcome.

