## 16.1.3 Significant protocol deviations

- The subject does not meet any of the inclusion criteria or meets any of the exclusion criteria but is included in the trial.
- (2) Subjects, who meet the criteria for discontinuation during the trial, do not withdraw from the trial. Conditions that should lead to premature discontinuation of the trial include: laboratory test becomes significantly abnormal; the patient withdraws consent; the patient is pregnant; the patient experiences an endpoint event or the patient does not meet criteria to enter the next phase of the study.
- (3) The examination on safety indicators, primary efficacy indicator or key secondary efficacy indicator are not conducted as required by the protocol, thus affecting the scientificity of the study. Including: ① The above examinations are performed outside the time window specified in the protocol, which constitute an important protocol deviation when the data of the primary or key secondary efficacy indicators become inappropriate for statistical analysis; ② The specific requirements of the protocol for examination operation are not met; ③ The examination of safety indicators is not performed, which makes the patient faces safety risks.
- (4) The subject receives incorrect investigational device to the extent that it affects the subject safety or statistical analysis. For example, the device model does not match the use.
- (5) Any serious violation of the principles of GCP in the implementation of the protocol. The main categories include: ① inappropriate process of obtaining informed consent, such as obtaining informed consent by unauthorized researchers; failure to obtain informed consent from patients again or serious delay in obtaining informed consent again after the update of informed consent version; irregular completion/signing of informed consent form (e.g., incomplete signature/date, selection of questions not completed by subjects themselves, signing untrue dates, etc.); existing evidence indicating that the

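### Withdrawing subjects after a staple-line SAE can remove the patients who matter most from the drainage >7 days comparison, and it conflicts with the plan's own follow-up rules

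*Combined protocol and SAP*

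**What the plan says.** Three rules point towards withdrawal.

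- Section 8.1.6.9, drop-out criterion (3): "If the subject experiences a serious adverse event (SAE), the investigator should withdraw the subject from the clinical trial".
- Section 8.1.8(5), Incidence of SAEs: "The adverse events related to the staple line during clinical trial shall be considered as serious adverse events". The one exception is that staple-line repair "is not repeatedly considered a serious adverse event".
- Section 16.1.3(2) lists as a significant deviation: "Subjects, who meet the criteria for discontinuation during the trial, do not withdraw from the trial". The conditions it gives for discontinuation include "the patient experiences an endpoint event". The term is not defined.

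Two rules point towards continued follow-up.

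- Section 14.1.3, on adverse events and SAEs: "Subjects occurring such event shall be followed up to end of the trial or the adverse event outcome".
- Section 8.1.6.7 requires the outcome of any adverse event to be observed.

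Section 8.1.6.9 also asks the investigator to contact a drop-out and complete whatever evaluations are still possible. It does not require Visit 3 (Day 7) or Visit 4 (Day 30).

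On analysis, section 9.7.2(4) states: "Missing values of secondary evaluation indicators shall not be estimated". Item (3) says the same of the primary indicator, while item (6) imputes missing safety values as worst case. Section 9.9 makes the PPS the primary population for efficacy analysis (it also mentions the FAS for efficacy evaluation) and the SS the primary population for safety. Section 9.4 lists failure to complete follow-up among the conditions that may take a subject out of the primary analysis.

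**The concern.** The stapler is used during one operation on Day 0. Withdrawing a subject afterwards stops no further study treatment; it mainly stops measurement. The trigger, a staple-line event, is a plausible predictor of the outcome still to be measured, so any resulting missing values would be informative.

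The outcome most affected is chest tube drainage beyond 7 days. Section 8.1.7.2(3) uses it as the substitute for staple-line healing, which cannot easily be observed. If subjects with staple-line problems have no recorded drain-removal date and nothing is estimated for them, the comparison is made among subjects whose staple lines gave no trouble. A real difference can then disappear. Section 9.5 reads p > 0.05 as no significant difference, so the loss favours a finding of similarity.

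The sponsor foresees that such withdrawals may be numerous: section 11.2 names excessive withdrawal for SAEs as a risk to the trial.

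**Working it through.** **1. Can the rules be triggered on Day 0?** Section 8.1.8(3) calls air leakage a common complication and assesses it in surgery by dripping saline on the staple line. If the investigator records a leak as a staple-line adverse event, section 8.1.8(5) makes it an SAE and section 8.1.6.9(3) calls for withdrawal, before drainage has been measured.

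**2. Which comparisons are exposed?**

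| Indicator | When assessed | If missing | Exposure |
|---|---|---|---|
| Primary success, dehiscence, air leakage | During surgery | Already recorded | None from missing values; for the primary, see step 5 |
| AE and SAE incidence | Whole trial, subject counted once | Triggering SAE already counts | Subject's status cannot change |
| Staple-line bleeding, infection | End of surgery to end of follow-up | Worst case, in the SS | Assumed events replace observation |
| Drainage >7 days | After surgery | Not estimated | Informative loss |

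**3. Drainage >7 days.** The documents give no leak rate and no drainage rate, so the rates here are assumptions. Let L be the leak rate, with drainage >7 days in 50% of leakers and 5% of others.

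- Everyone observed: rate = 0.50L + 0.05(1 − L).
- Leakers withdrawn and left out: rate = 0.05 in each arm.
- Leakers withdrawn but kept in the denominator, as the formula in section 8.1.7.2(3) literally reads: rate = 0.05(1 − L).

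| L, test v control | Everyone observed | Leakers left out | All in denominator |
|---|---|---|---|
| 20% v 10% | 14.0% v 9.5% | 5.0% v 5.0% | 4.0% v 4.5% |
| 15% v 8% | 11.8% v 8.6% | 5.0% v 5.0% | 4.3% v 4.6% |

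First row, test arm: 0.50 × 0.20 + 0.05 × 0.80 = 0.10 + 0.04 = 0.140. Control arm: 0.50 × 0.10 + 0.05 × 0.90 = 0.05 + 0.045 = 0.095. Subjects lost of 82 per arm: 82 × 0.20 ≈ 16 test and 82 × 0.10 ≈ 8 control.

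A second set of assumptions (SAE in 5% of control and 10 to 20% of test subjects; drainage >7 days in 40 to 80% of SAE subjects and 8% of others) gives true differences of 1.6 to 10.8 percentage points. All fall to zero when SAE subjects are left out.

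**4. Postoperative safety indicators.** Assume a true rate of 2% in both arms, SAE rates s of 5% control and 10% test, and all SAE subjects missing and imputed as events. Rate = s + 0.02(1 − s).

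- Control: 0.05 + 0.02 × 0.95 = 6.9%.
- Test: 0.10 + 0.02 × 0.90 = 11.8%.

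Here a difference appears where none exists.

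**5. The per-protocol route.** Under sections 8.1.7.1 and 9.5, a stapler-caused conversion is a primary failure and the primary comparison has a −10% margin. Such a subject plausibly has an endpoint event. If withdrawn, the subject may fail to complete follow-up and leave the primary analysis under section 9.4. If kept, the subject is a significant deviation under section 16.1.3, and section 9.9 excludes serious deviators from the PPS. The exemptions in section 16.1.5 do not clearly cover withdrawal by the investigator for an SAE.

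To show the possible size, take 82 per arm, true success of 97% control and 87% test (exactly at the margin), a Wald 95% interval (assumed; the plan names none), and a share f of failures in each arm leaving the PPS. Exact binomial enumeration gives the chance of wrongly declaring non-inferiority:

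- f = 0: 4.3% (above 2.5% because of the assumed Wald interval)
- f = 0.25: 12.5%
- f = 0.50: 35.9%

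**The case against.** A reader might infer that every subject with a staple-line problem must leave the trial and is lost from all the 7-day and 30-day comparisons. The documents do not support that.

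- Section 8.1.6.9 says should, not must, and repair is not counted again as an SAE. Whether a brief leak sealed on the table is an adverse event at all is a matter of interpretation.
- Missing safety values are imputed as worst case, and the SS needs only one treatment and one safety evaluation. Subjects missing for bleeding or infection are counted as events, not dropped.
- A subject withdrawn for an SAE already counts in AE and SAE incidence, and the intraoperative outcomes are already recorded.
- A site could partly satisfy both sets of rules by recording the drop-out, following the event and completing what it can. Section 14.1.3 allows follow-up to stop at the event's outcome.
- The endpoint-event wording looks like template text. The full phrase is "the patient experiences an endpoint event or the patient does not meet criteria to enter the next phase of the study", and this trial has no next phase.

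All of this stands, and it narrows the point. It does not remove it. A leak sealed on Day 0 may already have reached its outcome, so section 14.1.3 need not secure a drain-removal date, and the request to complete what is possible does not secure one either. Template wording still defines a significant deviation.

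Two further objections concern size. The fall to equal rates follows from giving non-leakers the same 5% in both arms; that is fair, and the tables show mechanism and direction, not a forecast. Also, with 82 per arm and complete data, a Pearson test of 14.0% v 9.5% reaches p < 0.05 in only about 14% of trials, and of 11.8% v 8.6% in about 10%. So p > 0.05 is likely either way. The harm is mainly to the estimated rates and to what a reader takes from them.

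**Conclusion.** The point holds in this form. Sections 8.1.6.9(3) and 16.1.3(2) conflict with sections 8.1.6.7 and 14.1.3, and the withdrawal rules select subjects by a staple-line event. Drainage >7 days is clearly exposed because it is measured after the trigger and is not imputed. On the assumed rates, a true difference of 4.5 percentage points (14.0% v 9.5%) vanishes, or changes sign slightly to 4.0% v 4.5%. The actual size depends on leak and drainage rates that the documents do not give, and on how strictly sites apply the withdrawal rule.

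For postoperative bleeding and infection the problem is different: worst-case imputation replaces observation with assumed events and can create a difference. For the primary comparison, loss from the PPS is a possibility under sections 9.4 and 9.9, not something the plan prescribes. It is still worth closing, because the false-positive risk rises quickly if even a quarter of failures leave the PPS.

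The matter should be settled in the wording, because outcome-dependent missing data cannot be recovered afterwards.

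**What to change.** 1. Reconcile sections 8.1.6.9(3) and 16.1.3(2) with sections 8.1.6.7 and 14.1.3, so that an SAE, a staple-line event or an endpoint event does not by itself end data collection. Define endpoint event or remove the term.
2. Require the drain-removal date and the already scheduled Visits 3 and 4 for every treated subject unless consent is withdrawn.
3. State in sections 9.4 and 9.9 that withdrawal after such an event does not remove a recorded primary outcome from the FAS or the PPS.
4. State the denominator for drainage >7 days and how a subject with no drain-removal date is handled.

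The laboratory-abnormality criterion in section 16.1.3(2) is not part of this argument. It and the clinical care of any event remain with the investigator and the sponsor.

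The cost is protocol wording only, since section 8.2.7 already schedules the visits for every subject. Reported drainage rates may be slightly less favourable.
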